5.2 Secondary Objectives and Endpoints

The secondary objectives of this clinical investigation are:

- To evaluate the performance of PAPIX ACNE SCAR in the prevention and improvement of acne scars after 2 and 8 weeks of treatment. This endpoint will be assessed as the proportion of subjects with improved acne scars and marks with respect to baseline and, at the same time, without any new facial acne scars after 2 and 8 weeks of treatment. The improvement of acne scars and marks will be assessed as the change in the qualitative Scar Global Assessment (SGA) by Goodman and Baron (2006) [26] between baseline and Week 2 and 8. The number of acne scars, to identify any new scars, will be assessed through the scars count and comparison with baseline.
- To evaluate the performance of PAPIX ACNE SCAR in the prevention of acne lesions after 2, 4 and 8 weeks of treatment. The number of acne lesions, to identify any new lesions, will be assessed through the lesions count and comparison with baseline.
- To evaluate the improvement in acne severity after 2, 4 and 8 weeks of treatment, through the Investigator Global Assessment, ranging from 0 (clear; clear skin with no lesions) to 4 (severe; many inflammatory and non-inflammatory lesions).
- To evaluate the improvement of the skin roughness on a 4-point scale from 0 (none; very smooth) to 3 (severe; very rough) after 2, 4 and 8 weeks of treatment.
- To evaluate the improvement of the skin texture on a 6-point scale from 0 (worse) to 5 (complete improvement), after 2, 4 and 8 weeks of treatment.
- To evaluate the subject's adherence to treatment by the product accountability and information asked to the subject.
- To evaluate the subject's and Investigator's global evaluation of satisfaction with regards to the performance of PAPIX ACNE SCAR, through a specific questionnaire.
- To evaluate the subject's overall acceptability of the treatment, through a specific questionnaire.

5.3 Tolerability and Safety Objectives

To evaluate the local and general tolerability of PAPIX ACNE SCAR.

Adverse events and adverse reactions will be recorded and evaluated.

6. Design of the Clinical Investigation

6.1 General

This is a multicenter, open label, uncontrolled, post-market clinical follow-up investigation.

All the subjects will be allocated to the following treatment group:

- PAPIX ACNE SCAR, topically applied twice a day for 8 weeks.

The subject will start treatment on the first day of study and will go on until 8 weeks after the first administration.

Each subject for whom written consent is obtained will be assigned a five-digit screening code, consisting of the site code (01 or 02) and a progressive number within the site: for example the first subject screened at site 01 will be assigned the code 01-001, the second one 01-002 etc.

All screened subjects will receive the code irrespective of whether or not they will receive the treatment. If a subject discontinues from the study at any time, the code will not be re-used.

All subjects who will sign the informed consent and receive the screening code will be entered into a Subject's Register, containing the name and surname of the patients and their Screening numbers. The Subject's Register will be accessible for source data verification but will be preserved only at clinical site.

Once eligibility of a patient is established (see Inclusion/Exclusion Criteria) the study treatment will be assigned.

The Investigator will keep record of all enrolled patients in the Subject's Screening/Enrolment Log: the subject screening number, the date of consent, the treatment assigned to the patient, if applicable, or the reason for not actively entering the study will be recorded.

6.2 Investigational device

6.2.1 PAPIX ACNE SCAR

The product under investigation is PAPIX ACNE SCAR.

Manufacturer: Relife Srl, [name]

Formattato: Italiano (Italia)

Device Name:	PAPIX ACNE SCAR
Formulation:	silicone gel
Route of administration:	topical application on breached/compromised skin (body surface)
Composition:	Aqua, cyclopentasiloxane, dimethicone, glycerin, butylene glycol, polyacrylate-13, polysilicone-11, polyisobutene, Octyldodecyl lactate, Niacinamide, ethylexylglycerin, hydroxypropylmethylcellulose, citric acid, disodium phosphate, lactic acid, sodium hydroxide, polysorbate 20, malic acid, glycoproteins, tocopheryl acetate, xanthan gum, taurine, zinc gluconate, hexamidine diisethionate, decyl glucoside, hydrolyzed glycosaminoglycans, sodium hyaluronate, caprylyl glycol, Hexylene glycol, phenoxyethanol, copper gluconate, sodium PCA. It does not contain fragrance, parabens and alcohol. It is heavy metals tested.

PAPIX ACNE SCAR is a CE marked, Class IIa medical device. It contains silicones, humectant, emollient and film-forming protective ingredients. PAPIX ACNE SCAR is indicated in the symptomatic treatment of acneic skin while reducing the appearance of acne scars. It is a multi-action treatment, which it treats acneic skin, improves acne scar appearance and lighten dark spots, prevents the development of new acne lesions and scars.

PAPIX ACNE SCAR creates a sheer physical barrier that separates the skin from surrounding environment, useful for generating favorable conditions for the maintenance and/or recovery of the physiological cutaneous layer in case of acne lesion. It improves skin by keeping it hydrated. It works to prevent and reduce acne scars.

6.2.1.1 Packaging and labelling

PAPIX ACNE SCAR will be provided for the study by the Sponsor of this clinical investigation.

The study product shipment to the study site will be done only after the completion of all Ethics and Administrative procedures.

The product will be labeled as experimental treatment in accordance with applicable Good Manufacturing Practice (GMP, Annex 13).

The primary package is a tube containing 7 ml of gel. Subjects will receive a total of no. 6 tubes.

6.2.1.2 *Study device instructions for use*

Patients will be instructed to use PAPIX ACNE SCAR applied twice a day, in the morning and in the evening before bedtime, and massaged gently into the skin until absorbed. PAPIX ACNE SCAR shall be applied only on the lesions, where possible. The treatment duration will be of 8 weeks.

6.2.1.3 *Handling and storage*

It is the Investigator/Institution's responsibility to set up a system for handling the clinical investigation treatment, so as to ensure that:

- deliveries of product supply from the Sponsor are correctly received
- products are handled and stored safely and properly in a secured area
- treatments are only dispensed to study subjects in accordance with the clinical investigation plan
- any unused, used, partially used product is returned to the Investigator (including empty tubes).

The study product shall be carefully stored at the study site, in a safe area and separately from other devices/drugs/products. It shall be stored in a dry and cool place, away from direct sunlight or heat.

The pharmacist and/or the Investigator shall maintain records of the study products receipt by the study site and an updated inventory of the study product.

Treatments will be dispensed to the subjects enrolled in this clinical investigation only by authorized personnel.

After study conclusion, all unused study product shall be returned to the Sponsor or destroyed at site after written Sponsor approval.

6.2.1.4 *Study product accountability and compliance*

The Investigator is responsible for ensuring the accountability of the study product.

Accountability records will include:

- confirmation of product delivery and receipt to/at the clinical site
- records concerning the product delivery to each subject and the return from each subject
- the return to the Sponsor or alternative disposition of unused products.

The Investigator should maintain records that adequately document:

- that the subjects were provided with the quantities specified by the clinical investigation plan/amendment(s)
- that all study products provided by the Sponsor were fully reconciled.

Unused products must not be discarded or used for any purpose other than the present clinical investigation.

Products that have been allocated to one subject must not be re-dispensed to a different subject.

Subjects will be reminded of the importance of strictly complying with the instructions received from the Investigator and to return all unused treatment or empty tubes to the Investigator.

Compliance to the treatment will be visually checked by the Investigators when the subjects are bringing back to the site the used/unused products.

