6.4 Procedures

6.4.1 Study Visits and Assessments

Visit 1 screening – baseline- treatment start (day 1):

Subjects will be evaluated with regard to the inclusion and exclusion criteria that will allow their participation into the study.

Before any study specific evaluation is carried out, subjects will receive all the information about the study by the Investigators and will sign an informed consent form. In the case of minors, the informed consent form shall be signed by the parents or the guardian.

The following activities will be performed:

- Collection of information about demography
- Medical and surgical history
- Acne medical history (duration, previous treatments)
- Physical examination (only dermatologic)
- Face cutaneous examination:
 - type of skin (dry/normal/oily)
 - site of acne lesions (on the face) and count
 - acne scars count
 - acne scars global assessment by the SGA
 - acne global assessment by IGA
 - roughness and skin texture evaluations
- Photographs of the face
- Previous (in the 6 months before) and concomitant medications/treatments recording
- Inclusion/exclusion criteria assessment
- Study product delivery to subject and instructions on how to use it
- Recommendations for face cleaning to follow.

Recommendations for face cleaning to follow: throughout the study subjects will be required to avoid soap and use only the product Papix cleanser for their face. The product will be provided by the Sponsor of the study. No other cleanser other than the product provided by the Investigator will be permitted.

PAPIX ACNE SCAR application: apply twice a day for 8 weeks, 2 FTU (finger tip units) in the morning and in 2 FTU the evening before bedtime, on the face, and massaged gently into the skin until absorbed.

Visits 2 and 3 – follow-up (Day 14 ± 3 and 28 ± 3, respectively):

The following activities will be done at visit 2 and 3:

- Face cutaneous examination:
 - acne scars and lesions count
 - acne scars global assessment by the SGA
 - acne global assessment by IGA
 - roughness and skin texture evaluations
- Photographs of the face
- Changes in concomitant medications/treatments recording
- Study product collection and new delivery to subject (only at visit 3)
- Treatment adherence check with the subject
- Recommendations for face cleaning to follow
- Adverse events (occurred since previous visit) recording.

Visit 4 – End of treatment and end of study (Day 56 ±3):

The following activities will be done at visit 4:

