1.2 Version history of the Protocol

Version Number	Date	Description
1.0	02/12/2019	First version submitted
2.0	02/07/2020	The protocol was amended in order to correct the number of tubes of the investigational product dispensed to the study subject.

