11.3 Measurements of Treatment Compliance

Treatment compliance will be assessed through the counting of the number of applications performed. The following formula will be used:

 $\frac{Number of applications performed}{Number of applications planned} * 100$

The number of planned applications will be estimated on the basis of the treatment duration x 2 times.

Treatment compliance will be estimated separately for the two study periods: Visit 1 - Visit 3 and Visit 3 - Visit 4 and it will be described in the Listing 16.2.5.

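### The 42 ml supplied per subject cannot be checked against 2 FTU twice daily, two protocol sections instruct application differently, and the SAP's adherence measure cannot show how much gel was used

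*Protocol*

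**What the plan says.** **Supply.** Protocol 6.2.1.1: "The primary package is a tube containing 7 ml of gel. Subjects will receive a total of no. 6 tubes". SAP 1.2 gives the reason for protocol version 2.0 as the need to "correct the number of tubes of the investigational product dispensed to the study subject".

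**Amount and area.** Protocol 6.4.1, under Visit 1, instructs subjects to "apply twice a day for 8 weeks, 2 FTU (finger tip units) in the morning and in 2 FTU the evening before bedtime", and names the face as the site. Protocol 6.2.1.2 sets the same frequency and says "The treatment duration will be of 8 weeks". It gives no quantity and restricts the area: "PAPIX ACNE SCAR shall be applied only on the lesions, where possible".

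**Dispensing.** The flow chart (Table 1) shows product dispensed at Visits 1 and 3 and returned at Visits 3 and 4. Section 6.4.1 agrees: "Study product collection and new delivery to subject (only at visit 3". Neither place says how the six tubes are divided.

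**Adherence.** Both documents name a secondary endpoint of adherence assessed through product accountability. Protocol 7.3.5.2 plans two things: self-reported application numbers and a summary of accountability. SAP 11.4.2 keeps only the first. SAP 11.3 defines compliance as applications performed over applications planned, and "The number of planned applications will be estimated on the basis of the treatment duration x 2 times". Under SAP 9.1.3 a subject is compliant if at most 20% of expected applications were skipped, the investigator inspects returned tubes by eye, and returned product goes into Listing 16.2.5. SAP 12.1 states exposure as 56 days ± 3.

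**The concern.** An amount per application, a frequency and a duration imply a total. That total should agree with the product handed out, and here nobody can tell whether it does. The two application instructions also differ, so the intended amount is itself unclear.

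The primary claim concerns performance after 4 weeks of twice-daily use. If some subjects stretched the gel or ran out, the Week 4 and Week 8 results, and the safety results, would describe a smaller exposure that varies between subjects. The planned adherence measure would not separate these cases. A subject who stretches the gel looks fully adherent, and one who runs out looks non-compliant. The report could then attach its result to a regimen that was not the one applied.

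**Working it through.** **Inputs.** 6 tubes of 7 ml (Protocol 6.2.1.1). 2 FTU morning and 2 FTU evening (6.4.1), so 4 FTU per day. 56 days, with Visit 4 allowed from Day 53 to Day 59. The volume of one FTU, v, is not in the documents and is treated as an assumption. The plan's own figure of six tubes cannot be reproduced, because no supply calculation is given.

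**Break-even over the whole study.**
- Supply: 6 × 7 = 42 ml.
- Need: 4 × 56 = 224 FTU.
- Break-even: 42/224 = 0.1875 ml per FTU, which is 0.375 ml per application or 0.75 ml per day.
- At Day 53: 42/(4 × 53) = 0.198 ml. At Day 59: 42/(4 × 59) = 0.178 ml.

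These are upper limits. They presume that every tube is emptied and that no usable gel is lost when tubes are collected at Visit 3.

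**Coverage for an assumed v** (need = 224v; days = 42/(4v); coverage = 42/(224v)):

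| v (ml) | Need (ml) | 42 ml lasts (days) | Coverage |
|---|---|---|---|
| 0.10 | 22.4 | 105 | 188% |
| 0.15 | 33.6 | 70 | 125% |
| 0.20 | 44.8 | 52.5 | 94% |
| 0.25 | 56 | 42 | 75% |
| 0.50 | 112 | 21 | 37.5% |

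**Up to the primary visit.** Because some of the six tubes are delivered at Visit 3, at most five are in hand before it. Need to Day 28 is 4 × 28 = 112 FTU. Break-even is then:
- 5 tubes at Visit 1: 35/112 = 0.3125 ml
- 4 tubes: 28/112 = 0.25 ml
- 3 tubes: 21/112 = 0.1875 ml

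The split is an assumption in every line.

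**What the adherence formula sees.** Planned applications over 56 days are 56 × 2 = 112.
- A subject who applies half the amount at all 112 scores 112/112 = 100%.
- A subject who uses the full amount, has v = 0.25 ml and can draw on all the gel stops at day 42. That is 84/112 = 75%, so 25% skipped, which is above the 20% limit although the instruction was followed until the gel was gone.

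**Where accountability goes.** Protocol 7.3.5.2 summarises it; SAP 9.1.3 lists it; SAP 11.4.2 omits it. SAP 11.5 and the title of Table 14.2.2.8 still carry the accountability name, but the analysis is a mean percentage, and the only percentage the SAP defines is the application ratio in 11.3. SAP 13 declares no departure from the protocol's analyses.

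**The case against.** A reader might infer that subjects would run out before Week 8, and probably before the Week 4 primary visit. The documents do not support that. They give no FTU volume, and for any value up to 0.1875 ml the supply is enough. A range that began at 0.25 ml would show only shortages and leave out every value at which the tubes suffice. A shortfall before Day 28 needs a second unstated figure, the tube split: with four tubes at Visit 1, even 0.25 ml per FTU lasts exactly 28 days.

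A reader might also take the amendment to the tube number as evidence that the number is still wrong. SAP 1.2 shows only that it was corrected. It is a reason to confirm the figure, not proof of error.

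The lesion-only instruction in 6.2.1.2 may mean less gel than a fixed 2 FTU on the face, so the 224 FTU need rests on 6.4.1 alone. That is fair, and it weakens any claim of a proven shortage. It does not settle the matter, because it leaves two instructions that may describe different exposures.

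On adherence, tubes are inspected and listed, and empty tubes would be noticed. That also stands: run-out is not invisible. What remains is that no summary or volume rule turns those observations into a result, and a smaller amount at each application leaves the count unchanged.

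Finally, the SAP describes enrolment as complete (Section 7), so a protocol clarification can no longer alter dispensing. The useful change is in the analysis and the report.

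**Conclusion.** Three things stand on the documents alone. The supply matches the FTU instruction only if one FTU is at most 0.1875 ml (0.178 ml if treatment runs to Day 59), and nothing provided lets anyone check that. Sections 6.2.1.2 and 6.4.1 differ on area, and only one states an amount. The endpoint named for product accountability is computed from self-reported application counts, which cannot show under-application, while the accountability summary planned in the protocol has become a listing.

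The size of any shortfall is unknown. Over the assumed 0.10 to 0.50 ml it runs from a surplus (188% coverage) to 37.5% coverage, and a gap before the primary visit is possible but not shown.

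Severity is moderate. The primary endpoint, the exact binomial test and the sample size are unaffected. What suffers is the description of the exposure that produced the results.

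**What to change.** **Protocol.** The sponsor should reconcile 6.2.1.1, 6.2.1.2, 6.4.1 and the product's Instructions for Use on four items: amount per application, area treated, ml per FTU for this tube, and tubes given at Visit 1 and at Visit 3. This review does not say which figure or instruction is right.

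**SAP 9.1.3, 11.3 and Table 14.2.2.8.** For Visit 1 to 3 and Visit 3 to 4 separately, add:
- tubes dispensed, returned unused, returned partly used and returned empty;
- a range of ml used per day, with the lower limit 7 × empty tubes and the upper limit 7 × (empty + partly used tubes), each divided by the days in the period. For illustration, 2 empty and 1 partly used tube over 28 days gives 14 to 21 ml, or 0.50 to 0.75 ml per day. Unreturned tubes should be counted separately;
- the number of subjects who returned only empty tubes.

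Keep the application count beside these. Where the reason is recorded, report applications missed because supply was exhausted apart from other skipped applications. The variable list in SAP 9.1 has no such reason, so this may not be possible for everyone.

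**Report.** Describe exposure by product used, not as 2 FTU twice daily, unless the figures are shown to agree.

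**Cost.** Small. Protocol 6.2.1.4 and Section 11 already require delivery and return records per subject, and 6.2.1.3 requires used, partly used and empty tubes to come back. Tube counts are coarse. If the condition of returned tubes was not recorded, the ml range widens. Reported exposure may look lower than the stated regimen.

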6.2.2 Concomitant Medications/Treatments

Any medications (other than those excluded by the clinical investigation plan) that were considered necessary for the patients' well-being and do not interfere with the study product can be given at the Investigator's discretion.

According to exclusion criteria, the following prior and concomitant medications are prohibited:

- topical treatments like antibiotics, corticosteroids, benzoyl peroxide, azelaic acid, hydroxy acids, retinoids and other anti-inflammatory drugs
- chemical peels
- systemic antibiotics, corticosteroids, spironolactone/drospirenone or immunomodulators, oral retinoids or cyproterone acetate/chlormadinone acetate;
- scrub, alpha hydroxy acid (AHA), skin irritant products;
- laser ablative procedures
- radiotherapies
- sun exposure (unless limited and with the use of protection cream SPF 50+) or tanning booths or UV sources.

The subject will be recommended not to use any other cleanser for the face than Papix cleanser, provided by the Investigator.

Any concomitant medication/treatment shall be recorded in the appropriate section of the CRF.

6.3 Subjects

In this clinical investigation 40 subjects will be enrolled fulfilling the following eligibility criteria.

6.3.1 Inclusion criteria

1. Subject's or parents or guardian (depending on the age of the subject) written informed consent obtained prior to any study-related procedures;
2. Male or female subjects aged ≥ 12 years of any race;
3. Subjects with any Fitzpatrick skin phototype;
4. Subjects with clinical diagnosis of mild to moderate acne vulgaris (IGA score 2 or 3) on the face
5. Presence of acne scars (all types included), of grade mild or moderate according to SGA;

6. Subjects with cooperative attitude, able to comprehend the full nature and the purpose of the investigation, including possible risks and side effects, and able to comply with the requirements of the entire investigation (including ability to attend the planned visits according to the time limits), based on Investigator's judgement.

6.3.2 *Exclusion criteria*

1. Pregnant women
2. Severe acne at inclusion or any acne requiring systemic treatment;
3. Presence of facial warts or fungal infections;
4. Active dermatitis on the face, rosacea, active herpes simplex;
5. Keloids presence in the area to be treated or keloids development during the treatment period;
6. History of radiation or skin tumors in the/close to the area to be treated in the past 5 years;
7. Laser ablative procedures within the last month;
8. Chemical peels within the last 6 months;
9. Use of topical treatments like antibiotics, corticosteroids, benzoyl peroxide, azelaic acid, hydroxy acids and other anti-inflammatory drugs within 2 weeks;
10. Use of topical retinoids within 4 weeks;
11. Use of systemic corticosteroids or antibiotics in the previous 30 days;
12. Use of systemic spironolactone/drospirenone or immunomodulators in the previous 3 months;
13. Use of oral retinoids or cyproterone acetate/chlormadinone acetate in the previous 6 months;
14. Use of scrub, alpha hydroxy acid (AHA), skin irritant products in the 2 days before study treatment start;
15. Subjects with any other clinically significant or unstable concurrent disease or skin condition or general condition that, in the Investigator's opinion, might interfere with the study evaluations;
16. Allergy, sensitivity or intolerance to the components of the investigational device formulations ingredients;
17. Concomitant or previous participation in other interventional clinical study in the past 3 months;
18. Subjects planning sun exposure or tanning booths or UV sources throughout the course of the study. In case of sun exposure this shall be limited and a protection cream (SPF 50+) shall be applied.

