Population	
The following populations are defined for this investigation:
 
•Safety analysis set (SAF): all patients enrolled who sign informed consent and receive at least one administration of the investigational device.•Full analysis set (FAS): all patients of the SAF who have performed the baseline assessments and have at least one post-baseline assessment of any performance endpoint.•Per-Protocol analysis set (PPAS): all patients of the FAS who meet all inclusion/exclusion criteria and who do not have any major protocol deviation. 
The analysis of safety endpoints will be performed in the Safety population (SAF). Analysis of performance endpoints will be performed on the FAS population. The analysis of primary endpoint will be repeated in the PPAS.

------------	--

Table 1: Study Flow-Chart

	Visit 1	Visit 2	Visit 3	Visit 4*
	Week 0	Week 2	Week 4	Week 8
	Day 1	Day 14 ± 3	Day 28 ± 3	Day 56 ± 3
	Screening Baseline Treatment start	Follow-up visit	Follow-up visit	End of treatment End of study
Written informed consent	✓			
Demographic data	✓			
Medical and surgical history	✓			
Physical examination (only dermatologic)	✓			✓
Inclusion and exclusion criteria	✓			
Acne scars and lesions count	✓	✓	✓	✓
Scars Global Assessment (SGA)	✓	✓	✓	✓
Acne Investigator Global Assessment (IGA)	✓	✓	✓	✓
Face photos	✓	✓	✓	✓
Skin evaluation (roughness, texture)	✓	✓	✓	✓
Study product dispensed	✓		✓	
Study product administration	→ (twice daily)			
Study product returned			✓	✓
Global evaluation of performance ¹				✓
Global evaluation of product acceptability ²				✓
Treatment compliance		✓	✓	✓
Concomitant medications/treatments	✓	✓	✓	✓
Local and general adverse events		✓	✓	✓

*Or Early termination Visit

¹To be evaluated by both the subject and the Investigator

²To be evaluated by the subject

2. Identification and Description of the Investigational Device

PAPIX ACNE SCAR is a silicone gel for acne lesions and scars. It is indicated to treat oily, blemished or acneic skin.

With regular use, PAPIX ACNE SCAR helps to improve acne skin and visibly improves the appearance of acne scars, while moisturising the skin. Thanks to its formulation, the medical device helps:

- improving acneic skin within 30 days;
- improving visible acne scars & marks;
- preventing the development of new acne lesions and scars.

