Scarring can occur as a result of damage to the skin during the healing of active acne, as scar formation is the normal and natural response of tissue to wound healing following an injury. The majority of people affected by acne scars have “atrophic scars” that are associated with a loss of collagen; a minority show “hypertrophic scars” and “keloids” [4], that are indeed characterized by more abundant collagen stretched and aligned in the same plane as the epidermis [5].

Early treatment of active acne remains the best way to prevent or limit acne-related scarring. It is also imperative to ensure active acne has been treated before approaching scar treatment so as not to create a cycle where active lesions continue to scar in areas already addressed [6]. The choice of agents used to treat acne involves the integration of multiple factors such as the severity of lesions present, duration of disease, past and present response to therapy, and tendency for scarring and post-inflammatory pigmentation. Therapy is therefore tailored to the individual patient depending on the nature and severity of their acne.

Oral antibiotics (e.g. tetracycline, minocycline, doxycycline, lymecycline) are highly effective for inflammatory acne and are widely used in clinical practice. Oral retinoids (retinol) are usually given in cases of severe acne, or for patients in whom inflammatory or pustular acne does not respond to other approaches [7].

Topical therapy is the standard of care for mild to moderate acne [8]. Many types of drugs are used, like antibiotics and retinoids, with other agents including benzoyl peroxide, salicylic acid, azelaic acid, and alpha-hydroxy acids [7]. Retinoids and antimicrobials such as benzoyl peroxide and antibiotics are the mainstay of topical acne therapy: such treatments are active at application sites, and they can prevent new lesions [9]. The main side effect is local irritation.

Gels, pledgets (medication-soaked pads), washes and solutions tend to be drying and are helpful for oily skin. Lotions, creams and ointments are beneficial for dry, easily irritated skin.

There are no general guidelines available to optimize acne scar treatment. However, there is a variety of therapies that may reduce the prominence of acne scars. The selection of an approach to treatment is based upon multiple factors such as the type and degree of acne scarring, patient preference, side effects, cost, and treatment availability [10].

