7.2 Definition of Study Populations for Analysis

The following populations are defined for this investigation:

- Safety analysis set (SAF): all patients enrolled who sign informed consent and receive at least one administration of the investigational device.
- Full analysis set (FAS): all patients of the SAF who have performed the baseline assessments and have at least one post-baseline assessment of any performance endpoint (primary or secondary).
- Per-Protocol analysis set (PPAS): all patients of the FAS who also meet all inclusion/exclusion criteria and who do not have any major protocol deviation (i.e. wrong inclusion, use of forbidden concomitant medications, etc.).

The analysis of safety endpoints will be performed in the Safety population (SAF). Analysis of performance endpoints will be performed on the FAS population. The analysis of primary endpoint will be repeated in the PPAS.

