8.2 Per-Protocol (PP) Population

The PP population includes all subjects of the FAS who also met all inclusion/exclusion criteria and who did not have any major protocol deviation (i.e. wrong inclusion, use of forbidden concomitant medications, etc.).

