10.2 Protocol Deviations

Protocol deviations will be reviewed and discussed with the sponsor before the database lock during Data Review Meeting.

Protocol deviations will be described in the Table 14.1.2 and in the Listing 16.2.2.

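### Does an exclusion criterion that covers keloids arising on treatment distort the per-protocol set?

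*Protocol*

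**What the plan says.** Criterion 5 appears in the same words in the Protocol Synopsis and in Protocol 6.3.2: "Keloids presence in the area to be treated or keloids development during the treatment period". The first half describes the skin at entry and the second describes something that happens later.

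The PP set is defined three times to the same effect. The Synopsis has "all patients of the FAS who meet all inclusion/exclusion criteria and who do not have any major protocol deviation", Protocol 7.2 has "all patients of the FAS who also meet all inclusion/exclusion criteria and who do not have any major protocol deviation", and SAP 8.2 has "subjects of the FAS who also met all inclusion/exclusion criteria and who did not have any major protocol deviation". None names a visit, and none treats criterion 5 separately. Protocol 7.2 and SAP 8.2 give two examples of a major deviation, a subject wrongly included and the use of a prohibited medication, and leave the list open.

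On timing, Protocol 6.4.1 says under Visit 1: "Subjects will be evaluated with regard to the inclusion and exclusion criteria that will allow their participation into the study". Table 1 ticks the eligibility criteria at Visit 1 only. Protocol 6.1 has treatment assigned once eligibility has been established. Protocol 6.3 says "40 subjects will be enrolled fulfilling the following eligibility criteria".

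On use, SAP 11.1 and 11.5 confine PP to a repeat of the primary endpoint. The primary test is on the FAS, whose definition (Protocol 7.2, SAP 8.1) contains no eligibility requirement. SAP 10.2 adds: "Protocol deviations will be reviewed and discussed with the sponsor before the database lock during Data Review Meeting".

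**The concern.** An analysis set should not be shaped by the outcome it is used to analyse. Success at Week 4 needs an improvement of at least one SGA grade and no new facial acne scar (SAP 11.4.1). Protocol section 3 lists keloids among the kinds of acne scar. If a new facial keloid adds to the scar count, a subject who develops one by Week 4 is a failure in the FAS. On the literal reading the same subject leaves PP, so the PP success rate rises because of a bad outcome.

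PP is the only planned supporting analysis of the primary endpoint. Its value lies in whether it agrees with the FAS, and that comparison is less clean if an on-treatment skin event decides who is in it. The study is also open label with a single arm, so whoever rules on membership can see the outcomes.

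**Working it through.** **1. The plan's own figure.** Inputs from Protocol 7.1 and SAP 7: null 0.50, alternative 0.75, two-sided 5% exact binomial test, 30 evaluable, 25% dropout.

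- Smallest r with P(X ≥ r | 30, 0.5) ≤ 0.025 is r = 21. The upper tail is 0.0214 (two-sided 0.0428).
- Power = P(X ≥ 21 | 30, 0.75) = 0.803, against the stated 80%.
- 30 / (1 − 0.25) = 40 enrolled.

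The stated design reproduces, and PP membership does not enter it.

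**2. The passages side by side.**

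| Supports eligibility at entry | Supports the literal reading |
|---|---|
| Treatment assigned after eligibility is established (Protocol 6.1) | Second half of criterion 5 |
| Criteria ticked at Visit 1 only (Table 1, Protocol 6.4.1) | PP definitions name no visit |
| Subjects enrolled as fulfilling the criteria (Protocol 6.3) | |
| Wrong inclusion given as a PP example (Protocol 7.2, SAP 8.2) | |

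No procedure re-assesses eligibility after Visit 1, so the plan describes no step at which the literal reading would operate.

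**3. Size if the literal reading were applied.** The documents give no keloid rate, so q below is an assumption. Each model tests PP at its own reduced size, with a true FAS success rate of 50%.

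- Model A: each failure is removed with probability q. Expected removals are n × 0.5 × q, which for n = 30 is 0.30 at q = 2% and 0.75 at q = 5%.
- Model B: a fraction q of all subjects is removed, and every one is a failure. Expected removals are n × q, which for n = 30 is 0.60 and 1.50. The PP success rate becomes 0.5 / (1 − q).

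Upper-tail rejection rate in PP (nominal limit 0.025):

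| n | q = 0 | A, 2% | A, 5% | B, 2% | B, 5% |
|---|---|---|---|---|---|
| 30 | 0.0214 | 0.0218 | 0.0239 | 0.0231 | 0.0301 |
| 40 | 0.0192 | 0.0200 | 0.0238 | 0.0222 | 0.0358 |

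Under model A, PP is significant while the FAS is not in 0.05% (q = 2%) to 0.25% (q = 5%) of trials at n = 30. Over all sizes from 30 to 40 the maximum is 1.2% (n = 39, q = 5%).

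The PP proportion under model A is π / (π + (1 − π)(1 − q)). For π = 0.50 it is 0.505 at 2% and 0.513 at 5%; for π = 0.75 it is 0.754 and 0.760. The shift is 0.4 to 1.3 percentage points.

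**4. Borderline results, in both directions** (two-sided exact p).

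- Failures removed: 20/30 (0.099) becomes 20/29 (0.061), then 20/28 (0.036). 26/40 (0.081) becomes 26/39 (0.053), then 26/38 (0.034). Two removals are needed at these sizes. At some others one is enough: 21/31 (0.071) becomes 21/30 (0.043).
- Success removed, as a keloid between Weeks 4 and 8 could do: 21/30 (0.043) becomes 20/29 (0.061). 27/40 (0.038) becomes 26/39 (0.053).

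**The case for a change.** The best case for acting is that the text does not impose the baseline reading. The example of wrong inclusion sits in the major-deviation clause, which is separate from the requirement to meet all criteria. The Data Review Meeting works to no written rule, and in an open-label study it may meet with outcomes in view. One sentence in SAP 8.2 before database lock would cost nothing, and under model B at 5% the PP error rate does pass 0.025.

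The textual point stands: criterion 5 does not fit an eligibility check made only at Visit 1. The 5% figure also stands as arithmetic. It requires one subject in twenty to develop a keloid in the treated area within the study, and each to be a Week-4 failure. Nothing in the documents supports that rate, and subjects with keloids already in the area are excluded.

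The rest carries less weight. Dependence on an on-treatment event is ordinary for a PP set, and this one already has it through prohibited medication. The overlap with the scar count is what would set a keloid apart, and the documents do not say whether a keloid is counted. The one-sentence remedy would not close the gap, because a keloid could still be ruled a major deviation under the open-ended list. SAP 7 reports the 40 subjects as already enrolled, so rewording the criterion could not alter entry. A removal should also be visible: SAP 16.2 plans listings of deviations, of subjects excluded from the efficacy analysis and of individual responses, so a reader could put the subject back.

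**Conclusion.** No change to the plan follows. Criterion 5 is loosely drafted, and its second half does not fit the Visit 1 check. Reconciling those passages is editorial, and nothing here bears on how an on-treatment keloid should be managed. For the analysis, the natural reading is eligibility at entry, and an analyst would apply it without being told.

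FAS membership, and so the primary test, is unaffected: at least 21 of 30, power 0.803. No decision rule rests on PP. If the literal reading were used, keloids in up to about 2% of subjects would raise the PP upper-tail error by at most 0.003 (0.0192 to 0.0222 at n = 40), and a late keloid would push the other way. Only a borderline PP result could change sides.

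This rests on two assumptions: keloids are rare over eight weeks, and a subject who develops one still has a Week-4 assessment. Protocol 16.1 does not name keloids as a reason for discontinuation. If a subject did leave before Week 4, missing data are not replaced (SAP 9.1.4), so the FAS result could lose that subject too. That would be a missing-data matter and not one of PP membership.
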